Bromhexine Hydrochloride Prophylaxis of COVID-19 for Medical Personnel: A Randomized

Open-Label Study

by [name], [name], [name], [name], [name], [name],

[name], [name]

SUPPLEMENTS. STUDY PROTOCOL

Almazov National Medical Research Centre

CLINICAL STUDY PROTOCOL

«Prophylaxis of SARS-CoV-2 infection and COVID-19 among medical personnel managing patients with the novel coronavirus disease »

Contents

1. Rationale	3
2. Purpose	4
3. Study type	4
4. Inclusion criteria	4
5. Exclusion criteria	4
6. Drop out criteria	5
7. Study design	5
8. Study endpoints	6
9. Randomization and sample size estimation	7
10. Bromhexine hydrochloride dosing and administration rules	8
11. Study timeline	8
12. Subject exclusion	9
13. Replacement of subjects when excluded from the study	9
14. Preliminary study termination	9
15. Safety reports	9
16. Ethics	9
Investigators	11

1. Rationale

Several independent scientific laboratories have analyzed data on the mechanism of action of drugs that block the transmembrane protease (TMPRSS2), which is necessary for the activation of the S protein of the coronavirus when it binds to the ACE2 receptor on the surface of epithelial cells. Currently, two drugs, potential TMPRSS2 inhibitors, are of particular interest: Camostat mesylate and Bromhexine hydrochloride [[name], P. Lierz; Frenxiv, April 23, 2020; Markus Hoffmann, Hannah Kleine-Weber, Simon Schroeder et al. Cell 181, 271-280 April 16, 2020; Kailas Sonawane Sagar S. Barale Maruti J. Dhanavade et al. ChemRxiv April 22, 2020].

These drugs are effective chemical TMPRSS2 blockers in vitro. According to the available data on severe acute respiratory syndrome caused by the SARS-CoV type coronavirus, the mechanism of entry into the cell of the new SARS-CoV-2 coronavirus is similar: it has been demonstrated in animal models that the introduction of SARS-CoV-2 into epithelial cells can be blocked by Camostat mesylate. In mice, Camostat, dosed at concentrations similar to clinically achievable concentrations in humans, reduced mortality after infection with SARS-CoV from 100% to 30-35% [Yanchen Zhou, Punitha Vedantham, Kai Lu et al. Protease inhibitors targeting coronavirus and filovirus entry. Antiviral Research 116 (2015) 76-84; Hoffmann M, Kleine-Weber H, Schroeder S et al. SARS-CoV-2 Cell Entry Depends on ACE2 and TMPRSS2 and Is Blocked by a Clinically Proven Protease Inhibitor. Cell. 2020; 181: 1-10].

Bromhexine, a well known pharmacological drug, is an alkaloid derived from Adhatoda vasca used as a secretolytic expectorant for the treatment of respiratory diseases with excessive or viscous mucus. Bromhexine stimulates the activity of the ciliated epithelium, enhances lysosomal activity and causes hydrolytic depolymerization of mucous protein fibers [Bhagat A, Rachana R. Bromhexine: A Comprehensive Review. Int J Bio Med Res. 2018; 9 (3): 6455-9]. The concentration of Bromhexine in the pulmonary parenchyma two hours after administration is 2.4-5.9 times higher than in the blood plasma. The drug demonstrates first-order pharmacokinetics and is almost completely metabolized to a variety of hydroxylated metabolites; the most famous of these is Ambroxol, also available as a licensed mucolytic drug.

Like Camostat, Bromhexine inhibits the activity of TMPRSS2, thus preventing the SARS-CoV-2 virus from entering the cell. Bromhexine blocks the ability of TMPRSS2 to activate the tissue zymogen precursor, plasminogen activator in vitro [Lucas JM, Heinlein C, Kim T, Hernandez SA, Malik MS, True LD et al. The Androgen-Regulated Protease TMPRSS2 Activates a Proteolytic Cascade Involving Components of the Tumor Microenvironment and Promotes Prostate Cancer Metastasis. Cancer Discovery. 2014; 4: 1310-25].

It is important to note that only minor side effects of Bromhexine have been described, such as nausea (a common effect), rash, bronchospasm, vomiting, diarrhea, and fever (noted as a rare effect). Severe complications, such as Stevens-Johnson syndrome, or toxic epidermal necrolysis, possibly associated with the metabolite Ambroxol, are casuistic (no more than 0.16 cases per million patients).

There are currently no results of prospective studies of the use of Bromhexine hydrochloride as a preventive measure. There is one known study planned in China (Evaluating the Efficacy and Safety of Bromhexine Hydrochloride Tablets Combined With Standard Treatment / Standard Treatment in Patients With Suspected and Mild Novel Coronavirus Pneumonia (COVID-19) clinicaltrials.gov: NCT04273763; sample of 60 patients, start date studies 02/16/2020 Two prospective placebo-controlled studies are also known to study the effect of

Camostat on reducing the severity of the incidence of COVID19: The Effect of Camostat Mesylate on COVID-19 Infection in Ambulatory Patients: An Investigator-Initiated Randomized, Placebo-Controlled, Phase IIa Trial, clinicaltrials.gov: NCT04353284, sample of 114 patients, study start date 04/30/2020 (Yale University, USA); The Impact of Camostat Mesilate on COVID-19 Infection: An Investigator-initiated Randomized, Placebo-controlled, Phase IIa Trial; clinicaltrials.gov: NCT04321096, sample of 180 patients, study start date - 03/31/2020 (Dani me, 9 participating centers).

We suggest, that when SARS-CoV-2 has already entered the cells, the effect of Bromhexine hydrochloride therapy will be low or insufficient. About 20-30% of medical personnel are infected with SARS-Cov-2. At the same time, there are similar data on the potential effectiveness of Bromhexine hydrochloride in the prevention of a new infection in risk groups from several independent groups of authors. According to data from personal communication with specialists in Germany, there were no cases of infection among those who took the drug prophylactically [Department of Anesthesiology, Intensive Care, Pain Management and Palliative Care, Marienkrankenhaus, Soest, Germany]. It can be assumed that there is a preventive effect of taking Bromhexine among medical personnel to reduce the risk of infection and COVID 19 disease, despite the use of personal protective equipment.

2. Purpose

To evaluate the efficacy and safety of oral administration of Bromhexine hydrochloride for the prevention of SARS-CoV-2 infection and COVID-19 disease in medical personnel managing patients with COVID-19

3. Study type

Prospective randomized open-label study with a control group, which assesses the superiority of prophylactic therapy

4. Inclusion criteria

- 1. Age \geq 18 years;
- 2. Negative test (PCR) for SARS-CoV-2 infection;
- 3. Absence of clinical manifestations of a respiratory infection;
- 4. Presumptive management of patients with laboratory and/or clinically confirmed COVID-19;
- 5. Signed informed consent to participate in the study.

5. Exclusion criteria

- 1. Intolerance to Bromhexine hydrochloride;
- 2. Work outside of contact with SARS-CoV-2 infection;
- 3. Pregnancy (positive laboratory test for pregnancy or ultrasound confirmation of pregnancy) and breastfeeding period;
- 4. Other circumstances that the researcher considers inappropriate to participate in this study.
- 5. Peptic ulcer or duodenal ulcer, incl. in anamnesis

6. Documented contact with a SARS-CoV-2 carrier or a COVID-19 patient within 14 days prior to randomization

6. Drop out criteria

1. Failure to comply with the rules for the use of personal protective equipment when working with SARS-CoV-2 infection (the rules for the use of PPE in accordance with the recommendations of the Ministry of Health of Russia and internal orders of the General Director of the V.A. research; control of the use of PPE - independent);

2. Any acute illness not associated with SARS-CoV-2 that occurred during the study period

[figure not shown]
7. Study design

[figure not shown]
This is single-center study. Location of the study center:

Almazov National Medical Research Centre; [name]

Study design is present on Figure 1.

• When COVID-19 is expected clinically or SARS-CoV-2 infection is verified with a positive PCR test, the endpoint is reached and the drug may be canceled;

• However, the drug can be continued at the request of the participant for mild and moderate forms of the disease, since, theoretically, a decrease in viral load is possible; patients with continued therapy will continue to be followed, but outside the study protocol.

The same test systems for PCR (SARS-CoV-2 infection) will be used during the study.

8. Study endpoints

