8.1 Primary endpoint

• Combined endpoint: a positive PCR swab test to SARS-CoV-a2 and/or clinically suspected COVID-19 at 4 weeks and/or after 14 days after the last contact with a SARS-CoV-2 positive person

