8.3 Methods for assessing primary and secondary endpoints

1. Clinical assessment of study participants for the presence of symptoms of respiratory infection

- 2. Laboratory diagnostics of the presence of SARS-CoV-2: swab PCR test;
- 3. Chest computed tomography, pulse oximetry to assess the severity of the disease;

4. Laboratory diagnostics of SARS-CoV-2 infection: plasma IgG;

5. Laboratory diagnostics of the severity of COVID-19: clinical blood test with leukocyte count, C-reactive protein, D-dimer, ALT, AST, bilirubin fraction; creatinine, urea, protein fractions; amylase; glucose;

6. The need for oxygen support and its type in the treatment of COVID-19; the duration of the need for oxygen therapy; duration of mechanical ventilation.

7. Working hours (hours) with patients with confirmed / suspected SARS-CoV-2 infection;

8. Additional observation of all study participants up to 8 weeks from the date of randomization.

Methodology for calculating the time of work with SARS-CoV-2 infection

1. Units of time calculation - hours;

2. Separately taken into account: a) the time of work in the therapeutic department, including the emergency room where patients with suspected / confirmed SARS-CoV-2 infection are located; b) the time of work in the intensive care unit, where patients with suspected / confirmed SARS-CoV-2 infection are located; c) the time of work in a "clean" area, outside the presence of patients with suspected / confirmed SARS-CoV-2 infection;

3. Working hours in the hospital without personal protective equipment in accordance with the regulations of Almazov National Medical Research Centre.

9. Randomization and sample size estimation

Randomization method: 1:1, allocation by minimization method to the preventive therapy group with Bromhexine hydrochloride and to the control group, taking into account the following factors: age (ranges 18-45, 45-64, 65-74, 75-79); type of contact with SARS-CoV-2 infection: ("red zone"; "green" zone); taking hydroxychloroquine to prevent COVID-19.

• "Red" zone: the closest and longest contact with SARS-CoV-2 infection associated with an infected aerosol (work in intensive care units and intensive care units; in operating and intervention laboratories; work with biological material of infected patients);

• Green Zone: work outside direct contact with patients with confirmed / suspected SARS-CoV-2 infection.

Known statistics:

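### The plan does not say whether Section 6 drop-outs are kept in the primary analysis; leaving them out of an open-label comparison could bias it in either direction

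*Combined protocol and SAP*

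**What the plan says.** Section 6 lists two drop-out criteria that operate after randomisation. The first is "Failure to comply with the rules for the use of personal protective equipment when working with SARS-CoV-2 infection", with the qualification "control of the use of PPE - independent". The second is "Any acute illness not associated with SARS-CoV-2 that occurred during the study period". The section does not say what happens to these participants' later tests or outcomes.

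Section 9 targets 118 people (59 per arm). It then raises this to 139 for a 15% loss, which it describes as covering loss after randomisation and illness other than SARS-CoV-2. Section 13 rules out replacement of excluded participants.

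Section 3 describes a "Prospective randomized open-label study with a control group, which assesses the superiority of prophylactic therapy". The composite primary endpoint in Section 8.1 is a positive PCR and/or "clinically suspected COVID-19 at 4 weeks", with a further time point counted from the last contact.

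On follow-up, Section 8.3 plans "Additional observation of all study participants up to 8 weeks from the date of randomization". Section 7 says that on suspected or verified infection "the endpoint is reached and the drug may be canceled". It adds, only for those who stay on the drug after that point, that "patients with continued therapy will continue to be followed, but outside the study protocol".

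The contents list has no statistical analysis section. Nothing in the text defines an analysis set or says that participants are analysed as randomised.

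**The concern.** Both Section 6 criteria can be related to the outcome. Breach of protective-equipment rules is plausibly linked to infection risk. Judging an acute illness to be unrelated to SARS-CoV-2 is the mirror image of judging it to be suspected COVID-19, which is an endpoint event. When PCR is negative, the same illness can go either way, and the person deciding may know the arm.

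If such people leave the analysis at different rates in the two arms, those who remain no longer form the randomised comparison. The error could create a benefit that is not there or hide one that is. With the analysis set unstated, it could also be chosen after open-label data have been seen.

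**Working it through.** **Inputs.** Section 9 gives event rates of 30% (control) and 10% (drug), 80% power, 5% alpha, 118 analysed and 139 randomised. Two-sided testing is my assumption, because the plan does not state sidedness. No exclusion rate by arm is given, so every exclusion rate below is also an assumption.

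**The plan's own figures.** With unpooled variance, n per arm = (1.960 + 0.842)² × (0.3×0.7 + 0.1×0.9) / 0.2² = 58.87, so 59 per arm and 118 in total. Then 118 / 0.85 = 138.8, so 139. Both match. Allowed loss is 139 − 118 = 21 people, or 10 to 11 per arm.

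**Model.** If a share m of would-be cases is excluded from an arm with true risk p, the observed risk is p(1 − m) / (1 − pm). For p = 0.30 this is 0.278, 0.255 and 0.231 at m = 0.1, 0.2 and 0.3. Rejection rates come from exact binomial enumeration of the uncorrected chi-square test at two-sided 5%, with 59 analysed per arm.

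**No drug effect (30% in both arms).**

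| Would-be cases excluded, drug v control | Favouring drug | Two-sided |
|---|---|---|
| none | 2.6% | 5.2% |
| 10% v 10% | 2.6% | 5.2% |
| 20% v 10% | 4.8% | 6.1% |
| 30% v 20% | 5.1% | 6.3% |
| 30% v 0% (extreme) | 13.7% | 13.9% |

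Head count: 69.5 × 0.30 × m is about 2, 4 and 6 people at m = 0.1, 0.2 and 0.3. The extreme row therefore needs about 6 of the 10 to 11 drug-arm drop-outs to be would-be cases, and none in the control arm.

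**Planned effect (30% v 10%).** Power is 80.5% with no exclusion.

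| Cases excluded, drug v control | Power |
|---|---|
| 10% v 10% | 77.8% |
| 20% v 20% | 74.3% |
| 10% v 20% | 68.3% |
| 20% v 30% | 63.0% |

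So of the fall from 80.5% to 68.3%, equal 10% exclusion alone accounts for 80.5 − 77.8 = 2.7 points.

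**Tipping point.** The planned result is about 6/59 v 18/59 (0.10 × 59 = 5.9; 0.30 × 59 = 17.7), chi-square p = 0.006. Now add the 21 drop-outs, split 10/11 or 11/10, with these numbers of cases among them:

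| Cases among drop-outs, drug v control | p (two splits) |
|---|---|
| 0 v 0 | 0.008, 0.006 |
| 3 v 3 | 0.015, 0.012 |
| 5 v 3 | 0.049, 0.039 |
| 6 v 3 | 0.081, 0.066 |
| 3 v 0 | 0.059, 0.049 |
| 4 v 0 | 0.099, 0.083 |

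**Power with all 139 analysed.** If a share r of the drug arm reverts to the control rate, drug-arm risk is 0.10(1 − r) + 0.30r, that is 10%, 11%, 12% and 13% at r = 0, 5, 10 and 15%. Exact power against 30% is about 86%, 81%, 76% and 70%.

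**The case against.** The strongest reply is that much of this is already covered. Section 8.3 observes all participants to 8 weeks from randomisation and makes no exception for drop-outs. This supports continued follow-up and partly answers that half of the point. It does not say whether drop-outs enter the primary analysis.

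Second, the 15% allowance and the no-replacement rule fit two readings: removal of drop-outs, or an analysis of everyone randomised with some outcomes missing. This stands. A reader might infer that the plan prescribes removal, but it only points that way.

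Third, discretion is narrower than it first appears. PCR is scheduled at days 0, 7, 14, 21 and 28 and in weeks 5-8. Clinical follow-up is daily, and laboratory and CT work-up are available when infection is suspected. A positive PCR is an endpoint, so for the acute-illness criterion only PCR-negative illness is open to judgement, and its share is not given. Control of protective-equipment use is called independent. These features reduce the risk but do not define the analysis set. The illustrations treat all cases as equally removable and so may overstate the acute-illness route.

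Fourth, a reader might infer from Section 12, which lists suspected or confirmed infection as a withdrawal criterion, that endpoint cases are themselves lost. Section 7 says the endpoint is reached at that moment, so withdrawal after the event has been counted is the natural reading.

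Finally, Figure 1 and another figure beside Section 6 were not shown in the text available for this review. They may show the handling of drop-outs, and their absence here is not held against the plan.

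**Conclusion.** The point holds as an unstated primary analysis set, combined with drop-out criteria that can be related to the outcome in an open-label trial. Bias is possible in either direction. Its size and sign depend on who is excluded from each arm, which the documents cannot show.

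On the illustrations, modest imbalance has little effect on two-sided error (5.2% to 6.1% or 6.3%), although most of the shift favours the drug. Equal exclusion of 10% leaves the error rate at 5.2%. At the planned effect the result survives balanced cases among the drop-outs and is lost only with a marked imbalance, such as 6 v 3 or 4 v 0; 3 v 0 is borderline.

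A reader might take the 13.9% extreme, or the whole fall in power to 68.3%, as the expected harm. The documents support neither. The first requires exclusions of would-be cases in one arm only, and part of the second arises even when exclusion is equal.

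This is worth correcting before the analysis because the remedy is cheap, not because a large bias has been shown. Confidence is medium.

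**What to change.** Leave the Section 6 and Section 12 criteria and the treatment-stopping rules as they are. Add wording that:

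- drop-outs who have not withdrawn consent continue the PCR and clinical follow-up already scheduled in Section 11;
- the primary analysis includes all randomised participants in their assigned arm;
- the analysis without Section 6 drop-outs is a sensitivity analysis;
- exclusions are reported by arm and reason.

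The cost is protocol text plus follow-up of about 21 people at existing visits. Classifying illnesses without knowledge of the arm would also help, but it may need extra staff and is a separate decision.

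The downside is possible dilution. Restate power for the all-randomised set: about 86% at the planned rates, and about 81%, 76% or 70% if 5%, 10% or 15% of the drug arm reverts to the control rate. At 10% or more, power is below the stated 80%. I would state that openly rather than enrol more participants.

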8.1 Primary endpoint

• Combined endpoint: a positive PCR swab test to SARS-CoV-a2 and/or clinically suspected COVID-19 at 4 weeks and/or after 14 days after the last contact with a SARS-CoV-2 positive person

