• The incidence rate of medical personnel working with SARS-CoV-2 infection: ranges between 20 and 50% (https://www.cdc.gov/mmwr/volumes/69/wr/mm6915e6.htm?deliveryName=USCDC_425-DM25898);

• Frequency of serious side effects of bromhexine hydrochloride: no more than 0.16 cases per million patients (Ambroxol and bromhexine containing medicinal products. EMA / PRAC / 800767/2015, 10/09/2015);

Estimated effect of preventive therapy:

Empirically, it is suggested that prophylactic drug administration can reduce the incidence of the primary endpoint by 20%.

Calculation of the study sample size:

• Power: 80%

• Confidence level - alpha error: 5%

• The incidence of the primary endpoint in the control group is estimated 30%; the incidence of the primary endpoint in the study group is estimated 10%;

• Thus, the target sample size: 118 people (59 subjects in each group)

• Estimated dropout rate from study protocol (dropout after randomization, non-SARS-CoV-2 incidence) 15%; thus, the required number of participants in the study will be 139 people;

10. Bromhexine hydrochloride dosing and administration rules

The drug is administered orally, after meals, without chewing, with plenty of liquid: 3 times a day, 8 mg.

In case of impaired renal function (creatinine clearance <30 ml / min / 1.73 m2) and / or liver insufficiency (an increase in the level of hepatic transaminases by 2 or more times), the drug should be discontinued in this study.

11. Study timeline

Evaluations	0	7 days	14 days	21 days	28 days	5-8 weeks		
Test (PCR) SARS- CoV-2	+	+	+	+	+	+		
Enzyme immunoassay - IgG to SARS- CoV-2	+*							
Clinical follow-up, daily	+	+	+	+	+	+		
Bromhexine hydrochloride administration, daily (8 mg 3 times a day)	+	+	+	+	+	+		
Individual protective equipment; daily	+	+	+	+	+	+		
Concomitant pharmacological treatment record	+	+	+	+	+	+		
Participant's questionnaire maintaining	+	+	+	+	+	+		
Laboratory diagnostics when SARS-CoV-2 is expected			When indicated					
Chest computed tomography when SARS-CoV-2 infection is expected				When indica	ted			

Table 1. Schedule of evaluations and prophylactic measures

*Plasma biobanking with subsequent IgG analysis when it is possible

12. Subject exclusion

Participants in the study can leave at any time, for any reason, without any consequences. A participant might be excluded from the study for a medical emergency.

Study participant specific withdrawal criteria:

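### The open-label primary endpoint counts undefined clinical suspicion of COVID-19, so unequal unblinded judgement can create or hide superiority

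*Combined protocol and SAP*

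**What the plan says.** - **Design (Section 3):** "Prospective randomized open-label study with a control group", testing superiority.
- **Primary endpoint (Section 8.1):** "a positive PCR swab test to SARS-CoV-a2 and/or clinically suspected COVID-19". Section 7 makes either component sufficient: "When COVID-19 is expected clinically or SARS-CoV-2 infection is verified with a positive PCR test, the endpoint is reached".
- **How suspicion is assessed (Section 8.3):** "Clinical assessment of study participants for the presence of symptoms of respiratory infection". The section also lists PCR, CT, pulse oximetry and blood tests, but ties CT, oximetry and most of the blood tests to severity. The text contains no symptom list, no threshold and no arm-blind assessor.
- **The competing label (Section 6):** a participant drops out for "Any acute illness not associated with SARS-CoV-2 that occurred during the study period".
- **Sample size (Section 9):** control incidence 30%, bromhexine 10%, 59 per group. The loss allowance, in per cent, reads "Estimated dropout rate from study protocol (dropout after randomization, non-SARS-CoV-2 incidence) 15", which brings enrolment to 139.
- **Analysis set:** none is stated, and the contents list has no statistical analysis section. Section 8.3 does plan observation of every participant to 8 weeks.
- **Secondary endpoints (Section 8.2):** two of them require a positive PCR, namely time to positive swab and time to PCR-positive symptoms.

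**The concern.** Take a participant with a respiratory illness and a negative swab. If someone who knows the arm suspects COVID-19, the participant counts as a primary event. If the same person judges the illness unrelated to SARS-CoV-2, the participant is a drop-out. Nothing in the text fixes that choice, and it may be made differently in the two arms.

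The primary comparison could then partly measure who was called suspected and not who was infected. The planned effect is small in absolute terms: 59 x 0.30 = 17.7 events against 59 x 0.10 = 5.9, about 12 events. A few relabelled illnesses per arm therefore matter. Bias can go either way: a false superiority claim, or a real effect that is missed.

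**Working it through.** **1. The plan's own figure.** For 30% v 10%, two-sided 5% and 80% power, (1.960 + 0.842)² = 7.849, and

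n = 7.849 x (0.30 x 0.70 + 0.10 x 0.90) / 0.20² = 7.849 x 0.30 / 0.04 = 58.9, so 59 per group, 118 in total.

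118 / 0.85 = 138.8, so 139. The sample size reproduces. The checks below use 69 per arm.

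**2. Model.** Let p be the share PCR-positive, i the share of PCR-negative participants with an illness that could be taken for COVID-19, and q the share of those illnesses called suspected. In each arm:

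- event probability e = p + (1 - p) x i x q
- drop-out probability d = (1 - p) x i x (1 - q)
- event rate with drop-outs removed = e / (1 - d); with all randomised kept as non-events = e

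Section 1 supports p of 20-30%: "About 20-30% of medical personnel are infected with SARS-Cov-2". The documents give neither i nor q, so both are assumptions. With p = 20% and i = 10%, 69 x 0.80 x 0.10 = 5.5 people per arm are open to either label.

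**3. Worked example, no true effect, p = 20%, i = 10%, q = 25% (bromhexine) v 75% (control).**

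- Bromhexine: e = 0.22, d = 0.06, rate 0.22 / 0.94 = 23.4%.
- Control: e = 0.26, d = 0.02, rate 0.26 / 0.98 = 26.5%.
- Gap with drop-outs removed: 3.1 points. Gap with all randomised: 26 - 22 = 4.0 points.

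Keeping everyone widens the gap if the case rule is not fixed, because the illnesses not called suspected stay in as non-events, and there are more of them in the bromhexine arm.

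**4. False superiority.** Exact enumeration of event, non-event and drop-out counts; uncorrected pooled z-test, critical value 1.96 (nominal 2.5% one-sided). Splits are bromhexine v control.

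| p | i | 45 v 55, removed | 1/3 v 2/3, removed | 25 v 75, removed | 25 v 75, all randomised |
|---|---|---|---|---|---|
| 20% | 10% | 3.05% | 4.65% | 6.16% | 7.99% |
| 25% | 10% | 2.97% | 4.22% | 5.36% | 7.10% |
| 30% | 10% | 2.89% | 3.89% | 4.76% | 6.37% |
| 10% | 20% | 4.05% | 10.65% | 18.84% | 27.04% |

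A fixed rule applied equally to all randomised gives 2.40-2.55%, whatever share of other illness it counts.

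**5. Reverse split, with a true effect.** Assume 25% v 8.3% infected (the plan's three-to-one ratio) and i = 10%. With drop-outs removed, power is 63.6% at equal judgement, 50.5% if two thirds (bromhexine) v one third (control) are called suspected, and 44.0% at 75% v 25%.

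**6. Power under the fix.** Worst case: all 15% who leave treatment lose the whole effect from day 0. The bromhexine rate becomes 0.85 x 10% + 0.15 x 30% = 13%.

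- Composite, 30% v 13%, 69 per arm: 69.6% (undiluted 30% v 10%: 85.7%).
- For 80% power: 7.849 x (0.21 + 0.1131) / 0.17² = 7.849 x 0.3231 / 0.0289 = 87.7, so 88 per arm.
- PCR-confirmed only, same dilution: 53.8% if three quarters of events are confirmed (22.5% v 9.75%), 36.8% if half are (15% v 6.5%).

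**The case against.** The strongest reply is that labelling is not free. PCR is scheduled at every visit with the same test systems, CT and laboratory tests follow when infection is expected, and the PCR-based secondary endpoints in Section 8.2 give a check that labelling cannot touch. All this limits the problem. It does not protect the primary endpoint, because under Sections 7 and 8.1 a negative swab does not cancel a suspected case.

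A second reply is that the illness and labelling rates are invented. They are assumptions, and at a 45 v 55 split with 20-30% PCR-positive the inflation is only about half a percentage point. Section 6 also covers any acute illness, and much of that would never be taken for COVID-19; the rate i must be read as look-alike illness only. The documents, however, offer nothing that bounds the imbalance.

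Three stronger readings are tempting and are not supported:

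- *Drop-outs certainly leave the analysis, and this is the main source of bias.* The 15% allowance suggests removal, but no passage confirms it, and Section 8.3 observes everyone to 8 weeks. In the unequal-labelling cases above, removal gives a smaller error than keeping all randomised.
- *The bias favours bromhexine.* Nothing in the documents fixes the direction.
- *Withdrawal on suspected infection (Section 12) damages the primary result.* A suspected case is already a composite event, so later missed swabs affect only the PCR-based analyses.

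**Conclusion.** The concern holds, and the main defect is the undefined, unblinded suspicion component. The missing analysis set is a second gap, and closing it alone would not help.

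For 20-30% PCR-positive and 10% look-alike illness, false superiority with drop-outs removed is 2.9-3.1% at 45 v 55, 3.9-4.7% at one third v two thirds, and 4.8-6.2% at 25 v 75, against a nominal 2.5%. A reader might take 18.8-27.0% as the expected error. Those values need few infections, frequent other illness and a 25 v 75 split together. With equal judgement there is no material inflation.

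That the stated rules leave the primary result open to this bias follows from the text. Its size rests on assumed rates. Statements that something is absent refer to the text only, since Figure 1 is not shown.

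**What to change.** Adopt (1) and (2) together; (2) without (1) makes the error larger in the unequal-labelling cases above.

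1. In Section 8.1, define clinically suspected COVID-19 by recorded symptoms and test results. Apply that fixed rule to every participant's records without knowledge of arm.
2. State that the primary analysis includes all randomised participants as allocated. Use the Section 6 criteria only to define a secondary per-protocol set.
3. In Sections 7 and 12, separate stopping the drug from leaving follow-up, so that the PCR already scheduled continues. This serves the PCR-based analyses.
4. State one primary endpoint window. Section 8.1 joins four weeks and 14 days beyond last contact by and/or, while Section 11 schedules PCR to day 28 and again in weeks 5-8; these must be reconciled. Over that same window, prespecify PCR-confirmed infection in all randomised, with a stated rule for missing PCR, as a sensitivity analysis reported beside any superiority claim. It builds on the Section 8.2 endpoints. It also shows whether the result depends on unequal symptom reporting by participants who know their arm, which arm-blind review cannot undo.

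**Cost.** Wording, a short arm-blind review of recorded data, and scheduled swabs in people who might otherwise have left. The statistical cost is dilution: in the worst case in step 6 the composite falls below the stated 80% power. State that power and do not enrol more. The PCR-only analysis is weaker still, so the composite should stay primary and PCR-only significance should not be required.
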